5.4.2. Other efficacy measures

The Patient Global Impression of Severity (PGI-S) will be collected at baseline and at the last visits of the double-blind treatment (SP III), open-label treatment (SP IV), and post-treatment phase (SP V), respectively. In this single-item scale, patients rate the severity of their migraine condition on a scale ranging from “Normal, not at all ill”(coded as 1) to “extremely ill” (coded as 7).

Change from baseline in PGI-S scores will be analyzed.

5.4.3. Health Outcome Questionnaires

5.4.3.1. Migraine Specific Quality of Life (MSQ) v2.1

The MSQ v2.1 is a self-administered health status instrument that was developed to address physical and emotional limitations of specific concern to individuals suffering from migraine. The instrument was designed with a 4-week recall period. The instrument consists of 14 items that address 3 domains: 1) Role Function-Restrictive (7 questions), examines the degree to which performance of daily activities is limited by migraine; 2) Role Function-Preventive (4 questions), examines the degree to which performance of daily activities is prevented by migraine; 3) Emotional Function (3 questions), examines feelings of frustration and helplessness due to migraine.

Responses are given using a 6-point Likert-type scale, ranging from “none of the time” to “all of the time.” Pre-coded item values and final item values for each MSQ item response are shown in [Table CGAX. 5.3](#). All item values range from 1 to 6. Final item value will be used as for analysis with higher score reflecting better quality of life.

Table CGAX. 5.3 **Item Values for Migraine Specific Quality of Life (MSQ) Item Responses**

Response Categories	Pre-coded Item Value	Final Item Value
None of the time	1	6
A little bit of the time	2	5
Some of the time	3	4
A good bit of the time	4	3
Most of the time	5	2
All of the time	6	1

Questions 1 to 7 of the questionnaire will be grouped together as Role Function-Restrictive domain, questions 8 to 11 as Role Function-Preventive domain and questions 12 to 14 as the Emotional Function domain. In general, no imputation for missing values is necessary because the MSQ was collected using patient direct data entry on an electronic device which did not allow patients to skip items. Patient either completed the scale in its entirety or not at all.

The raw score of each domain will be calculated as the sum of the raw scores of each question in that domain, using imputed scores where applicable. Should it be the case that the number of missing responses was more than half the questions in that domain, meaning that imputation of missing scores will not be done, the raw score for that domain will not be calculated, hence missing.

If any of the Role Function-Restrictive, Role Function-Preventive or Emotional Function domain is missing, then the total score will be missing, otherwise, the total score will be calculated as the sum of Role Function-Restrictive, Role Function-Preventive, and Emotional Function domain scores.

In addition, the raw scores of each domain and the total score will be transformed to a 0 to 100 scale using the following formulae:

- Role Function-Restrictive (range of 7 to 42):

$$\frac{(raw\ score - 7) * 100}{35}$$

- Role Function-Preventive (range of 4 to 24):

$$\frac{(raw\ score - 4) * 100}{20}$$

- Emotional Function (range of 3 to 18):

$$\frac{(raw\ score - 3) * 100}{15}$$

- Total Score (range of 14 to 84):

$$\frac{(raw\ total\ score - 14) * 100}{70}$$

The transformed total score and domain scores will be analyzed.

5.4.3.2. Migraine Disability Assessment test (MIDAS)

The Migraine Disability Assessment questionnaire (MIDAS) is designed to quantify headache-related disability over a 3-month period. This instrument consists of 5 questions (Q1-Q5) and 2 additional questions (A and B). The questionnaire measures the impact that migraine headaches have on migraineurs' life, including days of work or school missed, days with productivity at work or school reduced to half or more, days with household work missed, days with productivity in household work reduced to half or more, and days missed family/social/leisure activities. Each question is answered as a numeric number of days during the past 3 months of assessment, ranging from 0 to 90. The answers to all 5 questions will be added up to a total MIDAS score. A higher value is indicative of more disability. This instrument is considered highly reliable and valid, and is correlated with clinical judgment regarding the need for medical care (Stewart et al. 1999, 2001). For clinical interpretability, 4 categorical grades were developed based on the total score: Grade I (0 to 5) is for little or no disability, Grade II (6 to 10) is for mild disability, Grade III (11 to 20) is for moderate disability, and Grade IV (21+) is for severe disability. The severe disability category has subsequently been subdivided into Grade IV-A (severe [21 to 40]) and Grade IV-B (very severe [41 to 270]) because a high proportion of patients with chronic migraine are in Grade IV (Blumenfeld et al. 2011).

No imputation is needed when calculating the total score as patients are not allowed to send partial data.

The MIDAS responders are defined as patients with $\geq 50\%$ improvement in the total MIDAS score.

The total MIDAS score, the raw score of each question, and the indicator of MIDAS responders will be analyzed.

5.4.3.3. Migraine Interictal Burden Scale (MIBS-4)

The MIBS-4 measures the burden related to headache in the time between attacks. The self-administered instrument consists of 4 items that address disruption at work and school, diminished family and social life, difficulty planning, and emotional difficulty. The questionnaire

specifically asks about the effect of the disease over the past 4 weeks on days without a headache attack. Response options include the following: don't know/not applicable, never, rarely, some of the time, much of the time, or most or all of the time.

Table CGAX. 5.4 Scores for Migraine Interictal Burden Scale (MIBS-4) Item Responses

Response Categories	Item Score
Don't know/not applicable	0
Never	0
Rarely	1
Some of the time	2
Much of the time	3
Most or all of the time	3

Each response has an associated numerical score, as shown in [Table CGAX. 5.4](#). With the summation across all 4 items, a total score ranges from 0 to 12, and the level of interictal burden is categorized into the following: 0 for none, 1 or 2 mild, 3 or 4 moderate, and >5 severe (Buse et al. 2007, 2009).

The total MIBS-4 score and the level of interictal burden will be analyzed.

5.4.3.4. Patient Health Questionnaire-9

The Patient Health Questionnaire-9 (PHQ-9) is a 9-item patient-completed instrument that was designed for detecting Major Depressive Disorder (MDD) and for measuring the severity of depressive symptoms (Kroenke et al. 2001). The 9 items address anhedonia; depressed mood; trouble sleeping; feeling tired; change in appetite; guilt, self-blame, or worthlessness; trouble concentrating; feeling slowed down or restless; and thoughts of being better off dead or hurting oneself. Each item is rated on a 4-point scale (0 = not at all, 1 = several days, 2 = more than half the days, 3 = nearly every day) based on symptoms over the past 2 weeks. The overall score ranges from 0 to 27, with the levels of depression severity defined as follows: 0 to 4 minimal, 5 to 9 mild, 10 to 14 moderate, 15 to 19 moderately severe, and 20 to 27 severe. Item 10 is rated as “not difficult at all”, “somewhat difficult”, “very difficult”, or “extremely difficult”. The instrument is considered reliable and valid for use in research and clinical settings (Kroenke et al. 2001), including in patients with migraine (Seo and Park 2015a).

The PHQ-9 total score and the level of depression severity will be analyzed.

5.4.3.5. 7-Item Generalized Anxiety Disorder Scale

The 7-item Generalized Anxiety Disorder Scale (GAD-7) is a 7-item patient-completed questionnaire that measures the severity of anxiety symptoms. This instrument addresses the

feelings of nervousness, uncontrollable worrying, excessive worrying, trouble relaxing, restlessness, irritability, and fearfulness. The patient identifies how much they have been bothered by these symptoms over the past 2 weeks. Each of the 7 items is rated on a 4-point scale (0 = not at all, 1 = several days, 2 = more than half the days, 3 = nearly every day), with total score ranging from 0 to 21. The levels of anxiety severity are defined as follows: 0 to 4 minimal, 5 to 9 mild, 10 to 14 moderate, and 15 to 21 severe. The instrument is considered reliable and valid for use in research and clinical settings (Spitzer et al. 2006), including in patients with migraine (Seo and Park 2015b).

Binary indicator of anxiety will be derived as “Yes” (1) if the total score is ≥ 10 ; “No” (0) otherwise (Spitzer et al. 2006).

The GAD-7 total score, the level of anxiety severity, and the binary indicator of anxiety will be analyzed.

5.4.4. Safety endpoints

Safety endpoints consist of the incidences of treatment emergent adverse events (TEAEs), serious adverse events (SAEs) and adverse events (AEs) leading to discontinuation, vital signs (blood pressure, pulse, and body temperature), weight, electrocardiograms (ECGs), and laboratory measures (chemistry, hematology, and urinalysis).

5.4.5. Immunogenicity Endpoints

Immunogenicity endpoints consist of the incidences of anti-drug antibodies (ADAs) in all trial patients at baseline (pre-existing ADAs), and in all trial patients at post-baseline (treatment emergent ADAs). An additional endpoint is the incidence of neutralizing antibodies (NAb) present in those trial patients with ADAs.

5.4.6. Pharmacokinetic Assessment

Pharmacokinetic assessments will be summarized in the PK/PD analysis plan.

6. A Priori Statistical Methods

6.1. General Considerations

Unless otherwise specified, efficacy analyses will be conducted on an intent-to-treat (ITT) population, which will include all patients who are randomized and received at least 1 dose of study drug. Patients in the ITT population will be analyzed according to the treatment group to which they are randomized. Safety analyses will be conducted on safety population, which is the same as the ITT population. Patients in the safety population will be analyzed according to the actual treatment the patient received.

There are 5 analysis populations defined:

Intent-to-treat (ITT) population: All patients who are randomized and receive at least 1 dose of study drug.

Safety population: This population is the same as the ITT population defined above.

Open-label treatment population: All patients who enter the open-label treatment phase as indicated by receiving any injections starting from Visit 7. Patients in the open-label treatment population will be analyzed as a single group as they start with the same treatment in the study period. Analyses for open-label phase only will be based on the open-label treatment population.

Post-treatment population: All patients who enter the post-treatment phase (Study Period V) as indicated by entering any post-treatment visit (telephone or office visit). Analyses for post-treatment phase only (that is, excluding earlier study periods) will be based on post-treatment population.

GMB-treated population: All patients who have exposure to galcanezumab (GMB). The GMB-treated population will be used for summaries for GMB-treated time.

GMB-treated time is the period during which a patient received GMB.

- For patients who receive GMB in the double-blind treatment period (SP III) only, GMB-treated time begins and ends in SP III.
- For patients who receive GMB in both treatment periods, GMB-treated time begins in SP III and extends through SP IV.
- For patients who receive placebo in the double-blind treatment period, GMB-treated time begins in SP IV.

Treatment effects will be evaluated based on an overall 2-sided significance level of 0.05 for all efficacy and safety analyses. The 95% confidence intervals (CIs) for the difference in least-square means (LSMeans) between treatment groups will be provided.

For continuous variables with repeated measures, change from baseline will be analyzed using a mixed model repeated measures (MMRM) analysis. An MMRM analysis refers to a restricted maximum likelihood (REML)-based, mixed-effects repeated measures analysis using all the longitudinal observations at each post-baseline visit.

For other continuous variables, the change from baseline to last-observation-carry-forward (LOCF) endpoint will be analyzed using an analysis of covariance (ANCOVA) model.

Unless otherwise specified, when ANCOVA model is used to analyze a continuous efficacy variable, type III sum-of-squares for the LSMMeans will be used for the statistical comparisons.

Binary variables with repeated measures will be analyzed in a generalized linear mixed models (GLIMMIX) as pseudo-likelihood-based mixed effects repeated measures analysis.

For categorical efficacy variables without repeated measures, comparisons between treatment groups will be performed using logistic regression model. For other categorical variables without repeated measures, comparisons between treatment groups will be performed using the Fisher's exact test. Unless specified otherwise, Fisher's exact test will be used for comparisons of categorical safety measures; logistic regression will be used for comparisons of post-baseline efficacy measures.

[Table CGAX. 6.1](#) describes the rules for determining the patient population and baseline and postbaseline observations for each study phase and type of analysis. When "last of Visit x-x" is used in the table, the last non-missing observation obtained in the visit interval will be used.

Any change to the data analysis methods described in the protocol will require an amendment ONLY if it changes a principal feature of the protocol. Any other change to the data analysis methods described in the protocol, and the justification for making the change, will be described in the clinical study report or SAP. Changes may only be made in the SAP prior to unblinding.

Additional exploratory analyses of the data will be conducted as deemed appropriate.

Statistical analysis of this study will be the responsibility of Eli Lilly and Company or designee. SAS® software will be used to perform most or all statistical analyses.

Table CGAX. 6.1 Patient Population with Baseline and Postbaseline Definitions by Study Period and Type of Analysis

Study Period/Analysis	Patient Population	Baseline Observation	Postbaseline Observation(s)
Study Period III			
Efficacy analyses (repeated measures) or average of observed monthly values	ITT population with a baseline and at least 1 postbaseline observation	Visit 3	All scheduled visits 3 < Visits ≤ 7
Efficacy analyses at LOCF endpoint		Visit 3	Last of Visit 3.01–7
Health outcome analyses (repeated measures)		Visit 3	All scheduled visits 3 < Visits ≤ 7
Health outcome analyses at LOCF endpoint or for average of observed monthly values		Visit 3	Last of Visit 3.01–7
Treatment-emergent adverse events	Safety population	All Visits 1–3*a	All Visits 3.01–7
Serious adverse events, discontinuations due to adverse events	Safety population	NA	All Visits 3.01–7
Treatment-emergent abnormal laboratory values	Safety population with normal (with respect to direction being analyzed) laboratory values at all non-missing baseline visits and who have at least 1 postbaseline observation	Low: Min of Visits 1–3 High: Max of Visits 1–3 Abnormal: All Visits 1–3	Low: Min of Visits 3.01–7 High: Max of Visits 3.01–7 Abnormal: All Visits 3.01–7
Treatment-emergent changes in temperature and weight	Safety population with a baseline and at least 1 postbaseline observation	Low: Min of Visits 1–3 High: Max of Visits 1–3	Low: Min of Visits 3.01–7 High: Max of Visits 3.01–7
Treatment-emergent changes in blood pressures, pulse, and ECGs	Safety population with a baseline and at least 1 postbaseline observation	Low: Last of Visits 1–3 High: Last of Visits 1–3	Low: Min of Visits 3.01–7 High: Max of Visits 3.01–7
Treatment-emergent immunogenicity	Safety population with a baseline and at least 1 postbaseline observation	Visit 3	All Visits 3.01–7
Continuous safety analyses (repeated measures)	Safety population with a baseline and at least 1 postbaseline observation	Last of Visits 1–3	All scheduled visits 3 < Visits ≤ 7
Continuous safety analyses – change from baseline to LOCF endpoint (ANCOVA)	Safety population with a baseline and at least 1 postbaseline observation	Last of Visits 1–3	Last of Visits 3.01–7

Patient Population with Baseline and Postbaseline Definitions by Study Period and Type of Analysis

Study Period/Analysis	Patient Population	Baseline Observation	Postbaseline Observation(s)
Study Period IV			
Maintenance of 50% Response	Open-label treatment population – GMB-treated patients with 50% response at month 3	Visit 3	All scheduled visits 7 < Visits ≤10
Treatment-emergent adverse events	Open-label treatment population	All Visits 1–7*a	All Visits 7.01–10
Serious adverse events, discontinuations due to adverse events	Open-label treatment population	NA	All Visits 7.01–10
Treatment-emergent abnormal laboratory values	Open-label treatment population with normal (with respect to direction being analyzed) laboratory values at all non-missing baseline visits and who have at least 1 postbaseline observation	Low: Min of Visits 1–7 High: Max of Visits 1–7 Abnormal: All Visits 1–7	Low: Min of Visits 7.01–10 High: Max of Visits 7.01–10 Abnormal: All Visits 7.01–10
Treatment-emergent changes in temperature and weight	Open-label treatment population with a baseline and at least 1 postbaseline observation	Low: Min of Visits 1–7 High: Max of Visits 1–7	Low: Min of Visits 7.01–10 High: Max of Visits 7.01–10
Treatment-emergent changes in blood pressures, pulse, and ECGs	Open-label treatment population with a baseline and at least 1 postbaseline observation	Low: Last of Visits 1–7 High: Last of Visits 1–7	Low: Min of Visits 7.01–10 High: Max of Visits 7.01–10
Continuous safety analyses – change from baseline to LOCF endpoint (ANCOVA)	Open-label treatment population with a baseline and at least 1 postbaseline observation	Last of Visits 1–7	Last of Visits 7.01–10
Study Periods III / IV Combined			
Efficacy/Health outcome analyses	ITT population with a baseline and at least 1 postbaseline observation	Visit 3	All scheduled visits 3 < Visits ≤10
Continuous safety analyses (repeated measures)	Safety population with a baseline and at least 1 postbaseline observation	Last of Visits 1–3	All scheduled visits 3 < Visits ≤10

Patient Population with Baseline and Postbaseline Definitions by Study Period and Type of Analysis

Study Period/Analysis	Patient Population	Baseline Observation	Postbaseline Observation(s)
Study Period V			
Post-treatment-emergent adverse events	Post-treatment population	All Visits 1–10*a	All Visits 10.01–12
Serious adverse events, discontinuations due to adverse events	Post-treatment population	NA	All Visits 10.01–12
Post-treatment-emergent abnormal laboratory values	Post-treatment population with normal (with respect to direction being analyzed) laboratory values at all non-missing baseline visits and who have at least 1 postbaseline observation	Low: Min of Visits 1–10 High: Max of Visits 1–10 Abnormal: All Visits 1–10	Low: Min of Visits 10.01–12 High: Max of Visits 10.01–12 Abnormal: All Visits 10.01–12
Post-treatment-emergent changes in temperature and weight	Post-treatment population with a baseline and at least 1 postbaseline observation	Low: Min of Visits 1–10 High: Max of Visits 1–10	Low: Min of Visits 10.01–12 High: Max of Visits 10.01–12
Post-treatment-emergent changes in blood pressures, pulse, and ECGs	Post-treatment population with a baseline and at least 1 postbaseline observation	Low: Last of Visits 1–10 High: Last of Visits 1–10	Low: Min of Visits 10.01–12 High: Max of Visits 10.01–12
Continuous safety analyses – change from baseline to LOCF endpoint (ANCOVA)	Post-treatment population with a baseline and at least 1 postbaseline observation	Last of Visits 1–10	Last of Visits 10.01–12
Study Periods III / IV / V Combined			
Efficacy/Health outcome analyses	ITT population with a baseline and at least 1 postbaseline observation	Visit 3	All scheduled visits $3 < \text{Visits} \leq 12$
Continuous safety analyses (repeated measures)	Safety population with a baseline and at least 1 postbaseline observation	Last of Visits 1–3	All scheduled visits $3 < \text{Visits} \leq 12$
Treatment-emergent immunogenicity	Safety population - GMB-treated patients with a baseline and at least 1 postbaseline observation	Visit 3	All Visits 3.01–12

Patient Population with Baseline and Postbaseline Definitions by Study Period and Type of Analysis

Study Period/Analysis	Patient Population	Baseline Observation	Postbaseline Observation(s)
GMB-Treated Time			
Treatment-emergent adverse events	GMB-treated population	All Visits 1–3 before double-blind phase dosing for patients treated with GMB during SP III; All Visits 1–7 before open-label phase dosing for patients treated with placebo during SP III*a	All visits after first dosing of GMB through Visit 10
Serious adverse events, discontinuations due to adverse events	GMB-treated population	NA	All visits after first dosing of GMB through Visit 10
Treatment-emergent abnormal laboratory values	GMB-treated population with normal (with respect to direction being analyzed) laboratory values at all non-missing baseline visits and who have at least 1 postbaseline observation	Visits 1–3 before double-blind phase dosing for patients treated with GMB during SP III; Visits 1–7 before open-label phase dosing for patients treated with placebo during SP III	All visits after first dosing of GMB through Visit 10: Visits 3.01–10 for GMB-treated patients during SP III; Visits 7.01–10 for placebo-treated patients during SP III
Treatment-emergent changes in temperature and weight	GMB-treated population with a baseline and at least 1 postbaseline observation	Min/max of Visits 1–3 before double-blind phase dosing for patients treated with GMB during SP III for low/high, respectively; Min/max of Visits 1–7 before open-label phase dosing for patients treated with placebo during SP III for low/high, respectively	Min/max of all visits after first dose of GMB through Visit 10 for low/high, respectively; Visits 3.01–10 for GMB-treated patients during SP III; Visits 7.01–10 for placebo-treated patients during SP III.

Patient Population with Baseline and Postbaseline Definitions by Study Period and Type of Analysis

Study Period/Analysis	Patient Population	Baseline Observation	Postbaseline Observation(s)
GMB-Treated Time			
Treatment-emergent changes in blood pressure, pulse, and ECGs	GMB-treated population with a baseline and at least 1 postbaseline observation	Last non-missing value from Visits 1–3 before double-blind phase dosing for patients treated with GMB during SP III; Last non-missing value from Visits 1–7 before open-label phase dosing for patients treated with placebo during SP III.	Min/max of all visits after first dosing of GMB through Visit 10 for low/high, respectively: Visits 3.01–10 for GMB-treated patients during SP III; Visits 7.01–10 for placebo-treated patients during SP III.
Treatment-emergent immunogenicity	GMB-treated population with a baseline and at least 1 postbaseline observation	Visit 3	All Visits 3.01–10

Abbreviations: AE = adverse event; ANCOVA = analysis of covariance; ECG = electrocardiogram; GMB = galcanezumab; ITT = intent-to-treat; LOCF = last observation carried forward; max = maximum; min = minimum; NA = not applicable; SP = study period.

*a, AEs that occurred on the visit date of Visit 3 or Visit 7 will be determined to be predose or after dose based on AE start time and the injection time: predose if AE start time is before the injection time and post dose if AE start time is after the injection time. Note: Visit 3.01 indicates the first unscheduled visit occurring after Visit 3 and prior to Visit 4. Visit 7.01 indicates the first unscheduled visit occurring after Visit 7 and prior to Visit 8.

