**Study Period IV:** Patients who complete the double-blind period of this study can opt to enter an open-label period (Study Period IV) for up to 3 months of treatment with 120-mg/month galcanezumab. Following completion of the double-blind period Visit 7 (Month 3) assessments and procedures, patients may enroll in the open-label period of the study and receive open-label study drug. Sites and patients will remain blinded to patients' previous treatment assignments. To preserve blinding at Visit 7, each patient in any treatment group will receive 2 injections: patients randomized to placebo will receive an initial loading dose of 240-mg galcanezumab (2 injections of 120-mg galcanezumab at Visit 7 only); patients randomized to galcanezumab will continue the dose of 120 mg but also receive 2 injections (1 placebo injection and 1 120-mg galcanezumab injection at Visit 7 only). All patients will remain at the office for a 30-minute post-injection observation at this visit. At Visit 8 and Visit 9, all patients will receive a dose of 120-mg galcanezumab. Patients will continue to have efficacy and safety assessed, including daily completion of the ePRO diary and headache medication log (see Section 2, Schedule of Activities). Patients may continue to take their allowed acute migraine or headache medication as in Study Period III.

**Study Period V:** Patients who complete open-label treatment phase or discontinue for any reason during Study Period III or IV must enter into Study Period V for assessment during washout of investigational study drug. During this 4-month phase, sites and patients will remain blinded to patients' treatment assignments. Patients will follow all study procedures during Study Period V but will not receive galcanezumab or placebo. After completion of Visit 10 (Month 6) assessments, if clinically warranted due to a worsening of symptoms, patients may start migraine prevention medications at the discretion of the investigator. The list of allowed preventive medications will be provided separately. At Visit 12 (Month 10), patients will return to the site for their last study visit and be discharged from the study.

Visit 11 (Month 8) will be a virtual visit through telephone by site staff and is to include a review of any spontaneously reported AEs, queries on concomitant medications, and ePRO diary entries since last visit.

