#### **10.3.4.1. Categorical Safety Variables**

Unless specified otherwise, the categorical safety analyses will include both scheduled and unscheduled visits.

Comparisons between treatment groups for all categorical safety measures will be made using the Fisher's exact test for Study Period III (double-blind treatment). Descriptive statistics only will be presented for the treatment groups in the open-label phase (Study Period IV) and in the post-treatment follow-up phase (Study Period V) with the post-treatment population.

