5.1. Summary of Study Design

Study CGAX is a Phase 3, multicenter, double-blind, randomized, placebo-controlled study of galcanezumab in patients with EM, who have 4 to 14 MHDs (with or without aura) per month. The study has 5 periods, including a prospective baseline phase to determine patient eligibility.

Figure CGAX. 5.1 illustrates the study design.

^aEligibility period determined between a minimum of 30 days and a maximum of 40 days. Investigators may have up to 5 additional days (beyond the 40 days) if needed to schedule patients' Visit 3 appointment.

^aPatients randomized to galcanezumab will receive a loading dose of 240 mg at the first injection only (Visit 3).

^b Visit 4 and Visit 11 will be telephone visits.

^c At Visit 7, patients randomized to placebo who enter the open-label extension will receive galcanezumab at a dose of 240 mg. Patients randomized to galcanezumab will continue the dose of 120 mg.

Abbreviations: SP = study period.

Figure CGAX. 5.1 Illustration of study design for Clinical Protocol I5Q-MC-CGAX

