5.3. Method of Assignment to Treatment

Following a prospective baseline (30 to 40 days) period, eligible patients will be randomized in a 1:1 ratio to receive placebo or 120 mg/month of galcanezumab (with a 240 mg loading dose at the first injection [administered as 2 injections of 120 mg at Visit 3]), respectively, and will begin a 3-month double-blind treatment phase. Patients who complete the double-blind period may enter a 3-month open-label extension phase during which all patients will receive galcanezumab 120 mg/month. At Visit 7, patients originally assigned to placebo will receive an initial loading dose of 240 mg galcanezumab; patients originally assigned to galcanezumab will continue the dose of 120 mg but will receive 2 injections (1 injection of 120 mg galcanezumab and 1 injection of placebo) to maintain blinding. At Visit 8 and Visit 9 of the open-label phase, all patients will receive a 120 mg dose of galcanezumab. All patients will be followed for a 4-month, post-treatment phase during which no study medication will be administered.

Patients who meet all criteria for enrollment will be randomized to double-blind treatment at Visit 3. Assignment to treatment groups will be determined by a computer-generated random sequence using an interactive web-response system (IWRS). The IWRS will be used to assign double-blind investigational product to each patient. Site personnel will confirm that they have located the correctly assigned package by entering the confirmation number found on the package into the IWRS.

To achieve between-group comparability, the randomization will be stratified by country and baseline migraine frequency (<8 MHDs versus \geq 8 MHDs). To ensure an appropriate balance of patients with low- and high-frequency MHDs, the sponsor will stop enrollment of low-frequency patients if the number exceeds an estimated 292.

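### The open-label maintenance-of-response analysis asks for a treatment contrast within one arm, and the stated reason for pooling the open-label population does not match the Visit 7 dosing

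*SAP*

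**What the plan says.** **Maintenance of response.** The tertiary endpoint in SAP 4 is a proportion. SAP 5.4.1.2 and the Study Period IV row of Table CGAX. 6.1 restrict it to patients who took galcanezumab in the double-blind phase, met the 50% criterion at Month 3 and entered the open-label phase. Early discontinuers count as non-responders. The method paragraph in SAP 6.10.3 covers this measure and the double-blind sustained-response measure in one sentence. For both it specifies a between-treatment difference from a logistic model with treatment, country and continuous baseline. Table CGAX. 6.2 repeats logistic regression for the open-label measure.

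**Pooling.** SAP 6.1 defines the open-label population by injections from Visit 7 onward and states: "Patients in the open-label treatment population will be analyzed as a single group as they start with the same treatment in the study period". SAP 5.3 says of this phase that "all patients will receive galcanezumab 120 mg/month", but also that at Visit 7 "patients originally assigned to placebo will receive an initial loading dose of 240 mg galcanezumab". Footnote c to the design figure in SAP 5.1 adds: "Patients randomized to galcanezumab will continue the dose of 120 mg". Protocol 5.1 (Study Period IV) agrees: "patients randomized to galcanezumab will continue the dose of 120 mg but also receive 2 injections".

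**Open-label safety.** Protocol 10.3.4.1 says: "Descriptive statistics only will be presented for the treatment groups in the open-label phase". In Table CGAX. 6.1 the Study Period IV baseline for adverse events is "All Visits 1–7*a", and for blood pressure, pulse and ECG it is "Low: Last of Visits 1–7 High: Last of Visits 1–7".

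**The concern.** A model that compares treatments needs at least two treatments in the data. The maintenance set contains one, so the analysis cannot be run as written. Someone would have to choose a replacement after the double-blind results are known.

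The pooling sentence rests on patients beginning the phase alike, and the first open-label dose is where the original arms differ. They also differ in prior exposure, and the open-label baseline absorbs that difference. At stake is whether a reader of the open-label safety tables can tell events on first exposure to galcanezumab from events on continued exposure.

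**Working it through.** The plan attaches no figure to either analysis, so there is none to reproduce.

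**1. Can the maintenance contrast be estimated?**

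Inputs: the analysis set from SAP 5.4.1.2 and Table CGAX. 6.1; the model terms from SAP 6.10.3; three countries (China, India, Russia) from Table CGAX. 6.5, hence two indicators.

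Model: logit(p) = β0 + β1·T + γ1·C1 + γ2·C2 + δ·B, which has five columns.

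Every included patient took galcanezumab in the double-blind phase, so T = 1 throughout and the treatment column equals the intercept column. The model reduces to logit(p) = (β0 + β1) + γ1·C1 + γ2·C2 + δ·B. Only the sum β0 + β1 is identified.

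- One arm (the open-label set): rank 4 of 5 columns, and still rank 4 after the treatment column is removed. A numerical check on 80 generated single-arm patients gave the same ranks.
- Two arms (the double-blind sustained-response set): rank 5 of 5.

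The sentence in SAP 6.10.3 therefore works for the first measure it names and fails for the second. The open-label proportion needs no treatment term and can be computed.

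**2. Do patients start the open-label phase alike?**

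Planned galcanezumab, assuming every scheduled dose is given:

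| | Former placebo | Former galcanezumab |
|---|---|---|
| Double-blind total | 0 mg | 240 + 120 + 120 = 480 mg |
| Visit 7 | 240 mg | 120 mg (plus one placebo injection) |
| Visits 8 and 9 | 120 + 120 mg | 120 + 120 mg |
| Open-label total | 480 mg | 360 mg |
| Cumulative to the end of the open-label phase | 0 + 480 = 480 mg | 480 + 360 = 840 mg |

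The doses match at Visits 8 and 9 but not at Visit 7, where the phase begins.

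**3. What does the baseline do to pooled rates?**

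Table CGAX. 6.1 has seven Study Period IV rows. Four are categorical safety rows with a Visits 1 to 7 baseline: treatment-emergent adverse events, laboratory values, temperature/weight, and blood pressure/pulse/ECG. Of the other three, maintenance uses Visit 3, serious events and discontinuations have no baseline, and continuous safety uses the last of Visits 1 to 7.

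For former placebo patients, Visits 1 to 7 are free of galcanezumab. For former galcanezumab patients, the adverse-event, laboratory and temperature/weight baselines include on-drug values. The blood pressure, pulse and ECG baseline is the last value, normally Visit 7, and so is itself on-drug.

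Under SAP 6.14.2, an event already seen at the same or greater severity in the baseline window is not treatment-emergent. Under SAP 6.14.3, an abnormal baseline value removes a patient from the denominator for that test and direction. Reactions to the drug in the double-blind phase are thus screened out of open-label rates in one arm and not the other, and the pooled rate combines the two.

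**The case against.** The doses do not conflict: the Protocol and SAP agree on what each arm receives at Visit 7. The same drug on a nominal 120 mg monthly regimen is a fair meaning of the same treatment. Pooled descriptive tables for an uncontrolled phase are ordinary practice. First exposure is compared with placebo in the double-blind phase, galcanezumab-treated time takes its baseline before each patient's first galcanezumab dose, and continuous safety has a combined double-blind/open-label analysis from a Visits 1 to 3 baseline. Original arm is known, and SAP 6.1 allows further exploratory analyses. The maintenance endpoint is tertiary and outside the gatekeeping sequence.

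Most of this stands and limits the size of the point. It does not rescue the word *start* in the pooling sentence. Galcanezumab-treated time runs from first dose through Visit 10 and does not give open-label rates by arm. Nothing in it answers the maintenance model.

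A reader might also infer that the SAP contradicts itself by reporting open-label disposition (6.5) and important deviations (6.16) by treatment group. Those outputs use the intent-to-treat population, to which the pooling rule does not apply. Open-label compliance (6.7) is by treatment group, but no population is named. Nor does Protocol 10.3.4.1 spell out table columns; its plural is consistent with by-arm display but does not prescribe it.

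**Conclusion.** The maintenance analysis is wrong as written. The planned treatment contrast is not estimable in the set the SAP defines. The severity is minor: only the contrast fails, and no wrong proportion would be reported. This assumes that patients were dosed as allocated; a few misallocated patients would not create a meaningful comparison.

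The pooling point is a smaller, inexpensive improvement. The reason given in SAP 6.1 does not match the Visit 7 dosing, and the passages must be reconciled. A reader might infer that pooling is invalid or that it biases the open-label results by some amount. The documents do not support that: the open-label comparison is descriptive and no event rates are given, so no size is claimed. What follows is that four categorical safety rows cannot, as planned, be split into first-exposure and continued-exposure rates.

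The primary analysis, gatekeeping and sample size are unaffected.

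**What to change.** 1. In SAP 6.10.3 and Table CGAX. 6.2, limit the logistic treatment comparison to the two-arm sustained-response endpoint of the double-blind phase. Report open-label maintenance as a proportion with an exact 95% confidence interval, counting early discontinuers as non-responders as SAP 5.4.1.2 already requires.
2. In SAP 6.1, reconcile the reason for pooling with SAP 5.1, SAP 5.3 and Protocol 5.1.
3. Show open-label treatment-emergent adverse events, laboratory values, temperature/weight and blood pressure/pulse/ECG descriptively by original randomized arm plus a total.

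The cost is SAP wording, a few extra table columns and one interval in place of a model; no new data are needed. SAP 6.1 allows SAP changes only before unblinding, and SAP 3 places Version 1 before unblinding at the primary lock. If that point has passed, describe and justify the change in the clinical study report. The full open-label data are reported at the second lock.
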